[figure not shown]
UNIVERSITY OF ROCHESTER CANCER CENTER

**A Pilot Study of the Effects of High-Dose Oral Calcitriol and Physical Activity
on Bone Health in Breast Cancer Survivors**

STUDY CHAIR: [name].

Study Schema.....	3
1.0 Background	4
2.0 Objectives	11
3.0 Subject Eligibility	11
4.0 Treatment Assignment	13
5.0 Treatment Protocol.....	15
6.0 Treatment Evaluation	25
7.0 Statistical Considerations	29
8.0 Records to be Kept.....	31
9.0 Patient Consent and Peer Judgment.....	32
10.0 References.....	32

Study Schema

Both the calcitriol and exercise interventions are aimed at reducing fracture risk by maintaining proper bone density, thereby preventing osteoporotic/osteopenic conditions and increasing muscle mass. Both calcitriol and exercise are efficacious in maintaining proper bone health and muscle mass among the general population, but little research has been done on breast cancer patients and survivors. The combination of calcitriol and exercise, which function through different but similar mechanisms, could produce interactive effects in reducing fracture risk among breast cancer survivors.

Hypothesis: A combination of calcitriol 45 µg/week along with a structured home-based walking and progressive resistance exercise program will be efficacious in preventing bone resorption, as defined by NTx level, and in increasing bone formation, as defined by BAP level, among survivors of invasive breast cancer.

Primary Objective

To collect data on the efficacy and feasibility of a 12-week supplementation of calcitriol 45 µg with/without an accompanying

structured home-based walking/progressive resistance exercise program for improving bone health among breast cancer survivors.

Secondary Objectives

To collect data on the efficacy and feasibility of a 12-week supplementation of calcitriol 45 µg with/without an accompanying structured home-based walking/progressive resistance exercise program for increasing **strength** among breast cancer survivors.

To collect data on the efficacy and feasibility of a 12-week supplementation of calcitriol 45 µg with/without an accompanying structured home-based walking/progressive resistance exercise program for improving **skeletal muscle mass** among breast cancer survivors.

The primary analyses will consist of calculating mean change scores (i.e., baseline assessment minus final assessment) and standard deviations for both NTx and BAP. In addition, a paired-sample t-test will be used to calculate the differences between the baseline and end of trial values for both BAP and NTx.

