1.3 Calcitriol and Bone Health

Calcitriol could prove to be a safe, low-cost treatment for preserving bone health in breast cancer patients. Human beings obtain Vitamin D from sunlight, food, and supplementation.²⁶ Vitamin D plays a vital role in maintaining proper bone health and works in conjunction with calcium. Higher levels of vitamin D have been shown to increase the intestinal absorption of calcium.²⁷ One study demonstrated that an increase in serum vitamin D produced a 45%-65% increase in intestinal absorption of calcium.²⁸ Although no consensus exists on optimal vitamin D levels, most experts agree a 25-hydroxyvitamin D level of less than 20 ng per milliliter is deficient.²⁹ Based on this level, it is estimated more than 1 billion people worldwide and between 40%-100% of elderly U.S. residents are vitamin D deficient.³⁰⁻³³ More than 50% of postmenopausal women already under treatment for osteoporosis have deficient vitamin D levels.^{34, 35}

Bone health is a major concern in women undergoing treatment and who have completed treatment for breast cancer. Cancer-treatment-induced bone loss (CTIBL) is a long-term side-effect of various breast cancer treatments.³⁶ Chemotherapy, hormone therapy, and irradiation frequently lead, either directly or indirectly, to bone mass depletion in breast cancer patients.³⁷ Studies have documented accelerated bone loss in breast cancer patients, and this bone loss frequently goes undiagnosed.³⁸⁻⁴⁰ Breast cancer survivors have greater bone loss than women of similar age who were not diagnosed with cancer.⁴¹⁻⁴³ Risk factors for bone loss are already present in many women prior to a breast cancer diagnosis.⁴⁴ Treating bone loss in a prophylactic manner leads to greater success than delayed treatment.^{45, 46} The Women's Health Initiative (WHI) and other

studies have found that postmenopausal breast cancer survivors had increased risk of fractures.⁴⁷⁻⁴⁹

[figure not shown]

Fig. 2. Extent of bone loss due to cancer therapy. Menopausal women lose bone at a rate of 1% to 2% yearly. Cancer treatments, such as aromatase inhibitor therapy and chemotherapy, accelerate this process, leading to significant bone loss and subsequent skeletal complications (39, 75-79). Adapted from Skeletal Complications Across the Cancer Continuum CME Lecture 2005 series with permission from the Postgraduate Institute for Medicine.

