2.0 Objectives

Both the calcitriol and exercise arms are aimed at reducing fracture risk by maintaining proper bone density, thereby preventing osteoporotic/osteopenic conditions and increasing muscle mass. Both calcitriol and exercise are efficacious in maintaining proper bone health and muscle mass among the general population, but little research has been done on breast cancer patients and survivors. The combination of calcitriol and exercise, which function through different but similar mechanisms, could produce interactive effects in reducing fracture risk among breast cancer survivors.

Hypothesis: A combination of calcitriol 45 µg/week along with a structured home-based walking and progressive resistance exercise program will be efficacious in preventing bone resorption, as defined by NTx level, and in increasing bone formation, as defined by BAP level, among survivors of invasive breast cancer.

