3.2 Women of child-bearing potential (i.e. women who are pre-menopausal or not

surgically sterile) must use acceptable contraceptive methods (abstinence, intrauterine device (IUD), or double barrier device) and must have a negative serum or urine pregnancy test within 1 week prior to beginning treatment on this trial. Contraceptive use needs to be continued at least 1 month after the trial has ended.

- 3.3 Must provide informed consent.
- 3.4 Must be willing to discontinue use of calcium and/or vitamin D supplements.
- 3.5 Participants must have an ionized serum calcium level within normal limits (1.19-1.29mmol/L) and a total corrected serum calcium of < 10.2mg/dl.
- 3.6 Must have a functional capacity rating of ≤ 2 on the Eastern Cooperative Oncology Group (ECOG) performance status when assessed at baseline.¹⁵⁴
- 3.7 Must have the approval of their treating physician (or physician's nurse practitioner or physician's assistant) to participate in sub-maximal physiological fitness testing and a low to moderate home-based walking and progressive resistance exercise program and to receive the 12-week supplementation of calcitriol 45 μ g. Participants assigned to either of the calcitriol treatment arms will be instructed to stop taking calcium and/or vitamin D supplements.
- 3.8 Must be less than five years from the diagnosis of breast cancer and have received chemotherapy, radiation therapy, and/or hormonal therapy. Chemotherapy and radiation therapy, if received, must have been completed prior to study enrollment. Hormonal therapy may be ongoing.

Exclusion Criteria:

- 3.9 Subjects with life-threatening conditions that would preclude them from breast cancer treatment including chronic cardiac failure, which is unstable despite medication use, uncontrolled hypertension, uncontrolled diabetes mellitus, or unstable coronary artery disease.
- 3.10 Patients who had a myocardial infarction within the past year.
- 3.11 Patients with severe metabolic disorders, which includes phenylketonuria (PKU), homocystinuria, and Fabry's disease, that would preclude them from taking calcitriol.
- 3.12 Patients with impaired renal function (CRCL < 60 mL/min) or who had kidney stones (calcium salt) within the past 5 years.
- 3.13 Patients with hypercalcemia (corrected serum Ca > 10.2 mg/dl) or a history of

hypercalcemia or vitamin D toxicity.

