7.0 Statistical Considerations

7.0 Primary measures and analyses:

- 7.0.1 Bone Resorption: NTX
- 7.0.2 Bone Formation: BAP

Since the primary objective of this pilot study is to gather preliminary efficacy and feasibility data for the development of a planned career development grant application, the primary analyses will consist of calculating mean change scores (i.e., baseline assessment minus final assessment) and standard deviations for the two variables above. In addition, a paired-sample t-test will be used to calculate the differences between the baseline and end of trial value for both BAP and NTX. An independent t-test will be used to calculate the difference between the baseline and end of trial value for both BAP and NTx between the trial arms. Lastly, ANCOVA models will be used for BAP and NTx with the addition of relevant covariates collected during the study. Results of these two analyses will be interpreted cautiously because of the limited sample size.

7.1 Secondary measures and analyses:

- 7.1.1 Physical Activity: ACLS and Pedometer
- 7.1.2 Aerobic Capacity: VO2max Treadmill Test
- 7.1.3 Muscular Fitness: Handgrip Dynamometer and 7-10 Repetition Maximum
- 7.1.4 Muscle Mass: Bioelectrical Impedance Analysis
- 7.1.5 Since the secondary aims relating to physical activity, aerobic capacity, muscular fitness, and muscle mass, respectively, are intended to gather preliminary efficacy data for the development of a planned K07 submission, the secondary analyses will consist of calculating mean change scores (e.g., baseline assessment subtracted from the final assessment, and baseline subtracted from the follow-up assessment), standard deviations, and correlations on these variables for the two study arms. Additional exploratory analyses will use mixed effects models, to compare mean bone health within the four treatment arms during the intervention time and follow-up period of the study. The mixed effects

[figure not shown]

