7.2 Sample Size

7.2.1 Seventy-two women (18 women per treatment arm) were selected as an adequate size to provide pilot data for subsequent studies.

7.2.1.1 Based on the enrollment numbers above, the study will be able to detect a 40% difference in effects size between bone resorption and formation with 80% statistical power between the groups. Below is a graph of various effect sizes and the corresponding statistical power.

7.2.2 Based on a discussion with breast cancer clinicians at the University of Rochester Medical Center about patient volume and projecting an accrual rate of 50%, it will take approximately ten months to enroll 72 women.

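### The schema and section 7.0 list different primary analyses, and neither says which result or arm contrast answers the hypothesis; the paired t-test that both name cannot separate a treatment effect from a change common to all arms

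*Combined protocol and SAP*

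**What the plan says.** The hypothesis, in the Study Schema and section 2.0, is that calcitriol plus exercise "will be efficacious in preventing bone resorption, as defined by NTx level, and in increasing bone formation, as defined by BAP level". Section 4.1.3 randomizes four arms, and arm 4 is usual care with a daily multivitamin. Section 7.2.1 plans 18 women per arm.

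The plan describes the primary analyses in two places:

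- **Study Schema.** Mean change scores and SDs for NTx and BAP, and then "a paired-sample t-test will be used to calculate the differences between the baseline and end of trial values for both BAP and NTx". No between-arm comparison is mentioned.
- **Section 7.0, primary measures and analyses.** The same change scores, and again "a paired-sample t-test will be used to calculate the differences between the baseline and end of trial value for both BAP and NTX". It then continues: "An independent t-test will be used to calculate the difference between the baseline and end of trial value" for both markers between the trial arms. ANCOVA follows, with covariates not named. A closing sentence says that two of the analyses will be read cautiously. Coming directly after the independent t-test and ANCOVA, it appears to refer to those two and not to the paired test.

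Section 7.1.5 adds exploratory mixed models that compare individual arms, with hormone therapy and baseline marker level as fixed effects. No section names a deciding contrast or ranks the paired result against the between-arm result.

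**The concern.** The trial has a randomized concurrent control, but the test listed first in both places, and the only one in the schema, does not use it. A paired test asks whether the mean change within one arm differs from zero. That mean is the treatment effect plus whatever would have happened anyway over 12 weeks, and one arm alone cannot split the two.

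Some shared change is possible in this population. Criterion 3.8 reads "Chemotherapy and radiation therapy, if received, must have been completed prior to study enrollment. Hormonal therapy may be ongoing", with no minimum interval since treatment and no requirement that hormonal therapy be stable. The Fig. 2 caption in section 1.3, after giving the menopausal rate of bone loss, says "Cancer treatments, such as aromatase inhibitor therapy and chemotherapy, accelerate this process".

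Section 7.0 says the results are to support a career development grant application. If a significant within-arm change in arm 1 or arm 3 were reported as preliminary efficacy when arm 4 had moved by a similar amount, the next trial would be justified and sized on the wrong quantity. Without a named contrast, any of the six pairwise comparisons among four arms, or any paired result, could be presented as the answer.

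**Working it through.** **1. The plan's own figure.** Section 7.2.1.1 states 80% power between groups for a 40% effect size, without giving the metric, test or alpha. Read as a one-way ANOVA of four groups with Cohen's f = 0.40, N = 72 and an assumed alpha of 0.05:

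- noncentrality = N × f² = 72 × 0.16 = 11.52, with 3 and 68 df
- power = 0.799, which reproduces the 80%.

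Read as a pairwise t-test, 18 vs 18 with d = 0.40 and two-sided 0.05, power is 0.215. The figure therefore fits an omnibus between-group test that section 7 does not list. On either reading the sizing was framed between groups, whereas the schema's test is within an arm.

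**2. The paired test under drift with no treatment effect.**

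Inputs: n = 18 per arm (7.2.1). Assumed: two-sided alpha 0.05, normally distributed change, no dropout, and the same drift g in every arm, in SDs of change. The documents give no value for g, so a range is shown.

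- Paired test: df = 18 − 1 = 17, noncentrality = g × √18 = 4.243g.
- Between-arm test: the shared drift cancels (g − g = 0), so noncentrality is 0.

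| Drift g | Noncentrality (paired) | Paired test rejects | Between-arm test rejects |
|---|---|---|---|
| 0 | 0 | 0.050 | 0.05 |
| 0.2 | 0.849 | 0.126 | 0.05 |
| 0.3 | 1.273 | 0.225 | 0.05 |
| 0.5 | 2.121 | 0.516 | 0.05 |
| 0.7 | 2.970 | 0.799 | 0.05 |

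These rates apply to each arm and each marker.

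**3. What the between-arm comparison costs.**

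- 95% half-width, within-arm: t(17) × SD/√18 = 2.110 × 0.2357 = 0.50 SD.
- 95% half-width, 18 vs 18: t(34) × SD × √(2/18) = 2.032 × 0.3333 = 0.68 SD, about 1.36 times as wide.
- Power for 18 vs 18 (df = 34, noncentrality = d × √(18/2) = 3d): 0.31 at d = 0.5, 0.53 at d = 0.7, 0.83 at d = 1.0. It reaches 0.80 at d = 0.96.

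**The case against.** The strongest reply is that the schema is a summary and section 7.0 is the statistical plan. Section 7.0 puts the independent t-test between arms and ANCOVA under the primary heading, and 7.1.5 adds models comparing individual arms. A reader of the schema alone might infer that the trial ignores its usual-care arm or cannot answer its hypothesis. The documents do not support that: the plan performs the comparison with arm 4 but does not give it priority.

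A reader might also infer that the markers are known to drift. They are not. Sections 1.2 and 1.3 give bone-mass loss per year, about 2% or 1% to 2% after menopause, and no 12-week change in NTx or BAP. Continuing bone loss is compatible with an NTx level that is raised but flat, and a treatment that lowered it would then show on a paired test. Staggered entry ("it will take approximately ten months to enroll 72 women") and varied treatment histories may add variance without moving the mean in one direction.

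A further inference would be that true prevention must read as no effect on the paired test. That needs NTx to rise under usual care and the treatment to offset the rise exactly, and the documents show neither. Prevention is also only the NTx half of the hypothesis; the BAP half is an increase.

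Finally, this is a pilot, and section 7 says its between-arm and secondary results will be read cautiously. That lowers the stakes. It does not settle which result is the efficacy result, and the caution does not clearly extend to the paired test.

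**Conclusion.** The concern holds in a limited form. The schema and section 7.0 list different primary analyses, and neither names the result or arm contrast that answers the hypothesis. The test common to both cannot distinguish treatment from a shared change.

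Under no treatment effect, its rejection rate would be 13% to 80% for an assumed common drift of 0.2 to 0.7 SD, against 5% for the between-arm test. These figures are conditional: they rest on n = 18 with no dropout, two-sided 0.05, normal changes and a drift that the documents do not supply. At zero drift the excess vanishes.

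This is a defect of priority and wording in a plan that already contains the right comparison. It is worth correcting before results are seen, because the choice of contrast is still open.

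**What to change.** Amend the Study Schema and section 7.0 so that they list the same primary analyses, and state:

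- The efficacy analysis is the between-arm comparison of NTx and BAP change against arm 4: arm 3 vs arm 4 for the stated hypothesis, arm 1 vs arm 4 for calcitriol alone.
- It is preferably done with the ANCOVA already planned, naming the baseline marker level as a covariate, and reported as an estimate with a 95% CI.
- Within-arm means, SDs and any paired t-tests are descriptive and will not be read as evidence of efficacy.
- Arm 4 receives a daily multivitamin containing vitamin D 10 µg and calcium 200 mg and may continue its usual calcium supplements (5.8.1). The contrast is therefore against that control, not an untreated natural course.

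In 7.2.1.1, name the effect metric, test and alpha behind the 80%.

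The cost is text only, with no new data or visits. The downside is precision: the unadjusted between-arm interval is about 1.36 times as wide as the within-arm one, and 18 vs 18 gives 80% power only for a difference of about 0.96 SD. That is why an estimate and interval should lead, not a p-value.

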1.0 Background

1.1 Incidence and Survival Rate for Invasive Breast Cancer

Breast cancer is, by far, the leading type of cancer among women in the United States, with an estimated 182,460 new cases in 2008 alone.¹ In addition to the incident cases of invasive breast cancer, 62,000 cases of cancer in situ will be diagnosed.² In 2008, breast cancer will claim the lives of 40,480 American women, which represents 15% of the total cancer deaths.³ In the United States, approximately 17% of breast cancer patients are under the age of 50 (premenopausal) at time of diagnosis, while the remaining 83% of patients are 50 years of age or older.⁴ The incidence rate for estrogen receptor positive (ER+) breast cancer is approximately 190 per 100,000 women, but the incidence rate for estrogen receptor negative (ER-) breast cancer is about 4 times less at 47 cases per 100,000 women. Overall, over 70% of all breast cancers display some sort of estrogen receptor activity.⁵ The mortality rate for breast cancer is lower than that for other cancer sites, with an overall 5-year survival of 89% for all stages of breast cancer and 98% for localized breast cancer.² Due to the decreasing mortality rate of cancer, there are more than 10 million cancer survivors in the United States alone and more than 2 million breast cancer survivors.^{6, 7} Because many of these survivors do not succumb to cancer, other health problems, such as bone loss, have become a concern.

1.2 Bone Health Complications in Breast Cancer Patients

We propose to conduct an efficacy and feasibility pilot of breast cancer patients studied over 12 successive weeks to determine whether breast cancer patients can safely participate in a high-dose oral calcitriol (a vitamin D analog) intervention. Additionally, we will evaluate the influence of the intervention on bone health biomarkers. Recently, the American Cancer Society joined the Canadian Cancer Society, along with 6 other health groups, in urging more vitamin D research.⁸ Numerous studies have demonstrated that proper supplementation with vitamin D and its main analog (calcitriol) can improve bone health in a wide variety of populations. The majority of trials have focused on post-menopausal women, who are generally at higher risk for bone loss. Peri-menopausal women lose 3%-5% of their bone mass annually, while postmenopausal women lose approximately 2% of their bone mass annually, compared with just 0.5% annual loss in men.^{9, 10} Progressive bone loss can lead to osteoporosis, a skeletal disorder characterized by diminished bone strength. Women with this condition are predisposed to increased risk of fracture, and this disorder can result in suffering and functional decline for the individual and drain health-care resources.¹¹

Treatment for various types of cancer can have deleterious effects on bone health. A 1990 study was one of the first to demonstrate that those who were treated for breast cancer had lower bone mineral density compared to women without cancer of similar age.¹² Other studies have shown that both pre and postmenopausal women treated for breast cancer have a significantly lower bone mineral density than women of similar age without breast cancer.¹³⁻¹⁵ Increased rates of bone loss and osteoporosis lead to increased fracture risk for many breast cancer survivors. A study from the Women's Health Initiative found that survivors of breast cancer were more likely to suffer an osteoporosis related fracture compared to women with no history of cancer.¹⁶ A 1999 study in the British Journal of Cancer found that women with breast cancer were almost 5 times more likely to suffer a fracture than healthy controls.¹⁷ The study also found women were more than 6 times more likely to suffer a fracture than controls. This evidence demonstrates that breast cancer survivors are more likely to have bone loss and fractures compared to women with no history of breast cancer.

In 2004, there were an estimated 10 million American women with osteoporosis and an addition 34 million women with its precursor, osteopenia.¹⁸ The effects of osteoporosis can be devastating. Every year, hip fractures are responsible for 300,000 hospitalizations.¹⁹ Studies have shown that up to 25% of the elderly who fracture a hip die within one year.²⁰ Over 30% of survivors will be permanently disabled, and approximately 20% of survivors will need long-term care in a nursing home.²¹⁻²⁴ The cost attributed to hip fractures can exceed \$80,000 per person and costs the United States between \$13 and \$25 billion annually, along with 550,000 years of lost life.²⁵

Table 5-3. Direct Health Care Expenditures for Care of Osteoporotic Fractures Among Persons ≥ 45 Years of Age in the United States by Type of Service and Type of Fracture, 1995

Type of fracture	Type of service (millions of \$)						
	Inpatient hospital	Emergency room	Outpatient physician	Outpatient hospital	Other outpatient*	Nursing home	Total
Hip	5576	130	67	9	90	2811	8682
Forearm	183	55	93	8	4	41	385
Spine	575	20	13	3	10	126	746
All other sites†	2259	3632	297	45	91	899	3953
Total	8594	567	470	65	194	3875	13,764

*Includes home health care, ambulance services, and medical equipment.

† Depending on age, race, and gender, from 15% to 60% of all other fractures were attributed to osteoporosis

Source: Ray et al. 1997. Reproduced from *J Bone Miner Res* 1997; Jan; 12(1): 24-25 with permission of the American Society for Bone and Mineral Research.

